## 8.8. Quality control

Quality control measures encompass activities aiming at the preclusion of protocol violations and erroneous data capture and transmission. They include

- surveillance of collection of data within the specified window of time
- verification of accuracy, consistency and plausibility of eCRF data feeds
- consistent use of pre-programmed inherent data range and plausibility checks enabling prompt feedback and clarification of aberrant records
- strict assignment of roles and data access rights, thus ensuring the compliance with requirements of privacy and data protection

Monitoring site visits are not envisaged by default.

## 8.9. Limitations of the research methods

The selected endpoints are routinely used and the methodologies for their assessment have been comprehensively verified and proved to display predictive strength. However, it should be taken into consideration that the inherent high mortality risk might compromise the validity of mortality as a major endpoint. Simultaneous use of composite outcomes is deemed to ameliorate the assessment of the effects of therapeutic interventions [Goldstein et al., 2005; Nadel et al., 2007].

The current approach to scoring the severity of purpura-associated lesions employs arbitrary statements, which reflect the investigator's day-to-day impression [de Kleijn et al., 2003]; accordingly, large variations and limited possibility for quantitative comparisons should be expected. A descriptive lesion grading of the external appearance based on pictorial reference examples in the eCRF it is expected to provide at least a uniform description.

The endpoint 'length of hospital stay' will conceivably display large inter-individual variability, due to varying length of post-ICU recovery and immediately adjacent reconstructive surgical interventions. Nonetheless, this variable is expected to deliver important information on the economic burden of SAPF and its direct sequelae.

Despite encouraging evidence, the relevance of biochemical markers of inflammation in monitoring the effects of therapeutic interventions in sepsis remains ambiguous, mainly due to issues of sensitivity and specificity [Goldstein et al., 2005]. Still, in view of the undisputed role of inflammatory mediators in the pathogenesis of SAPF [Darmstadt, 1998], their measurement is justifiable.

The therapy of SAPF involves multi-pronged measures, which may obscure the "net effect" of an individual therapeutic agent. Thus, efficacy aspects of a given treatment have to be evaluated in conjunction with the co-medication used in the individual case; this circumstance, as well as the influence of concomitant medication, will be taken into consideration while designing the eCRF.

## 9. Protection of human subjects

The Registry protocol is subject to approval by the IRB of the Friedrich Schiller University, Jena, which will serve as the supervisory ethic institution in charge. Approval of the Registry protocol by the responsible regional or national authorities will be sought after by participating centers which are outside of the jurisdiction of the IRB in charge.

Eligibility for an individual treatment modality will be defined by the responsible physician by fulfillment of the criterion "manifest clinical signs of sepsis-associated *Purpura fulminans*". The probability of inclusion into the Registry will not influence the physician's decision on the use of a selected medication.

An informed consent, signed by the patient or his/her legal representative, also comprising collection and use of medical data, will be sought for before enrolment into the Registry. However, in view of the rarity of the disease and the high mortality, usage of deviant regional and national regulations will be considered where appropriate and legally acceptable.

The protection of participant's privacy will be warranted by **a)** pseudonymization of patient personal data at the participating center for the duration of the clinical observation period, **b)** data transmission using a secure password-protected login and **c)** ultimate anonymization of the collected information upon verification of data consistency and plausibility. The pseudonymous ID list will

assign a four-digit-number to each participant and contain a pre-defined minimum of personal information considered essential for the processing of queries pertaining to accuracy, plausibility and consistency. For the communication with the Data Management, only the assigned four-digit-numbers will be used. The identity a patient can be disclosed only to the authorized study team members at the participating sites. Personal identity data (i.e. the pseudonymous ID record) are subject to transformation upon confirmation of the completeness of relevant information by the Registry Data Management. Numbers assigned in the process of pseudonymization will be replaced by the Data Management, in order to abrogate the possibility of tracking back patient's identity, while retaining the possibility to allocate data to the center of origin. The primary ID lists at the participating sites will be stored for at least 10 years in a mode, which precludes access of non-authorized persons. Compliance with this requirement will be verified in the course of monitoring site visits.

The sovereignty over the Registry data is exerted by the Advisory Committee. Documentation will take place at the Center for Clinical Studies of the Jena University Hospital. Registry data will be processed automatically, with scheduled regular backups. Registry data are accessible to a limited number of staff members, who are directly involved in this project. Data media are stored in a secured space on the premises of the Center for Clinical Studies, with access permitted only to the system administrator.

Publication of Registry data will occur only in aggregated form, without disclosure of details of subjects and participating investigation sites. These conditions also apply to the dissemination of Registry data, e.g. on request of external investigators. In the latter case an approval of the IRB will be solicited.

The regulations pertaining to patients' welfare and privacy protection comply with the international and national norms and legislation (Helsinki Declaration, GCP, GEP national regulations of participating countries).

## **10. Management and reporting of adverse events/adverse reactions**

Considering the critical condition of patients with Purpura fulminans and their high disease-related mortality, the documentation and reporting of all adverse events (AE) and serious adverse events (SAE) occurring in these patients is beyond the scope of this registry.

In view of the complex pathology and the multitude of concomitantly used therapeutic agents in SAPF patients, registration of treatment-emergent adverse drug reactions (ADR) will be confined to those, which denote pathological alteration of the coagulation status. In this context, ADR of specific interest include

- bleeding (especially intracranial and in visceral organs)
- thrombotic events

Occurrence of adverse drug reactions (ADR) will be recorded by the study teams at the participating centers in the eCRF, with the local investigator being responsible for the assessment of the ADR. Severity of ADR will be assessed by means of a three-grade-scale (mild-moderate-severe). In view of the severity of the condition, however, it is predictably difficult to discern ADR of mild and moderate intensity.

Additionally an ADR Report Form for these assessments will be distributed to the local investigators as a part of the Investigator Site File (ISF). Documented treatment-related ADR or other safety

concerns (regardless of the expectedness or causality) will be forwarded by the local investigator by his own responsibility to the Marketing Authorization Holder of the presumably involved product and the Advisory Committee of the registry within 24 hours of awareness.

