## **11. Plans for disseminating and communicating study results**

A major objective of the Registry consists in accumulation and systematic evaluation of etiology, clinical course and treatment approaches of SAPF. The individual aspects of knowledge encompass (but are not restricted to):

- Gaining new insight into the causality of SAPF
- Comparative evaluation of currently used treatment strategies, especially those comprising use of anti-coagulant proteins
- Identification of patient clusters (e.g. by age, initial morbidity score, Purpura etiopathogenesis, concomitant therapy etc.) which display above-average responsiveness to anti-coagulant protein supplementation
- Disclosure of biomarkers which are particularly suitable for outcome prediction and dynamic monitoring of therapy
- Disclosure of unacquainted side-effects of therapeutic interventions

Registry data will be systematically scrutinized with regard to the above-listed issues and the results will be disseminated in aggregated form as

- Periodical (biannual) reports
- Hot-topic updates
- Safety information
- Publications
- Recommendations for the elaboration of uniform guidelines for SAPF

As improvement of quality aspects of treatment quality form a key objective of the Registry, the participating centers will be entitled to access their retrospective data in individual or aggregated form (before or upon completion of anonymization, respectively), and receive biannual summaries collating their performance to the average of all participants.

External interested parties may receive on demand and on condition of approval by the Advisory Committee and the IRB excerpts from Registry data pertaining to a previously defined topic.

Based on the results of biannual Registry evaluations and safety records, the Advisory Committee will compile and update recommendations for SAPF therapy, which will be distributed to the participating centers and interested external parties.

[figure not shown]

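### Section 11 promises a search of registry data for unknown side-effects of any kind, but Section 10 registers only coagulation-related reactions, so other reactions cannot be quantified

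*Combined protocol and SAP*

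**What the plan says.** Section 10 sets the recording rule in two steps. General safety documentation is left out: "the documentation and reporting of all adverse events (AE) and serious adverse events (SAE) occurring in these patients is beyond the scope of this registry". For suspected drug reactions, "registration of treatment-emergent adverse drug reactions (ADR) will be confined to those, which denote pathological alteration of the coagulation status", with bleeding and thrombotic events named as being of specific interest.

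Section 10 then describes a second channel with a wider scope. It takes in both documented reactions and any further worry about safety: "concerns (regardless of the expectedness or causality) will be forwarded by the local investigator by his own responsibility to the Marketing Authorization Holder". The registry's Advisory Committee is named as a second recipient, and the time limit is 24 hours.

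Section 11 lists among the registry's knowledge aims "Disclosure of unacquainted side-effects of therapeutic interventions". It states that "Registry data will be systematically scrutinized with regard to the above-listed issues", and it names safety information and biannual reports among the outputs. It also says that the Advisory Committee's therapy recommendations rest on the biannual evaluations together with safety records.

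Two other places describe the scope differently. Section 8.3 leaves the recording of treatment-related adverse events to the local investigator and puts emphasis on bleeding and thrombosis without restricting recording to them. The flowchart in Section 8.2 has one row for adverse drug reactions, ticked only at end of study, with no restriction by type.

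**The concern.** The Section 11 aim is to be met from registry data, and it is not limited to coagulation. Under Section 10, a suspected reaction of another kind, for example an allergic one, falls outside what is registered. The 24-hour channel covers such a reaction, but the plan does not say that the report becomes part of the dataset from which the biannual outputs are produced.

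What is at stake is how the safety outputs are read. The registry plans recommendations on the use of Protein C (Section 7) and on SAPF therapy generally (Section 11). An ADR table with no non-coagulation reactions would look reassuring when it only reflects the recording rule. Because Sections 8.3 and 10 differ, sites may also follow different rules, and even a small non-zero count would then be hard to interpret.

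**Working it through.** The plan states no figure for safety detection, so there is none to reproduce. The check is a comparison of the texts.

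**Scope by place**

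| Place | What is covered | Limited to coagulation? |
|---|---|---|
| Section 4, endpoints | Treatment-related adverse events, at the investigator's decision; bleeding and thrombosis listed | Only these two named |
| Section 8.2, flowchart | One adverse drug reaction row, end of study | No |
| Section 8.3 | Treatment-related adverse events, at the investigator's discretion | Emphasis only |
| Section 10, eCRF registration | Adverse drug reactions | Yes |
| Section 10, 24-hour forwarding | Documented reactions or other safety concerns | No |
| Section 11, aim | Unknown side-effects | No |

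**Following one event through the plan.** Take a suspected allergic reaction to a plasma product.

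1. Section 10 excludes it from registration, since it does not denote altered coagulation. Section 8.3 would let the investigator record it. The two rules give different answers.
2. Section 10 has it forwarded within 24 hours as a safety concern, so the Advisory Committee can learn of it.
3. No section says that the forwarded report is entered in the eCRF or joined to the patient's treatment record. Section 11 names safety records separately from the registry evaluations, which suggests a parallel stream.
4. The eCRF does hold exposure: the flowchart records treatments and cumulative doses, and Section 8.4 derives exposure from them. The denominator exists, but the plan does not connect these events to it.
5. The result is an individual report without a rate by product or a comparison with and without Protein C.

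**Illustration of size.** The number of patients is 50 per year × 3 years = 150 (Section 4, timetable). The risk p of a non-coagulation reaction is not in the documents. I assume 0.5% to 2%.

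Chance of at least one event in n patients = 1 − (1 − p)^n.

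- n = 150, p = 0.5%: 1 − 0.995^150 = 0.53
- n = 150, p = 2%: 1 − 0.98^150 = 0.95

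If half the patients receive Protein C (also assumed), n = 75:

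- p = 0.5%: 1 − 0.995^75 = 0.31
- p = 2%: 1 − 0.98^75 = 0.78

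These are chances that an event occurs, not that it is recognised and attributed to a product. They show only that such events could plausibly arise in a registry of this size. The finding does not depend on them.

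**The case against.** A reader might infer that the registry is unable to detect unknown harms at all. The documents do not support that. The 24-hour channel is worded "concerns (regardless of the expectedness or causality) will be forwarded by the local investigator" and reaches the registry's own Advisory Committee, which uses safety records when it compiles recommendations. An unexpected reaction can therefore surface as a single report, and an unknown effect on coagulation is within the registered scope anyway.

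Nor can one say that the eCRF has no field for other reactions. The eCRF is not in the documents, the flowchart row is unrestricted, and Section 8.3 speaks only of emphasis. Organ-level harm may also show indirectly, through SOFA or PELOD scores, laboratory values and renal replacement therapy, although not as an attributed reaction.

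The restriction is also a reasoned choice. Section 10 cites critical illness, complex pathology and many concurrent agents. The side-effect aim is not among the objectives in Sections 4 and 7, so correcting the Section 11 wording would be a legitimate response.

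All of this stands, and it limits the point to systematic capture and quantification. It does not remove the mismatch. Forwarding rests on the investigator's own responsibility, and Section 8.8 does not provide for monitoring visits by default. The report form is issued for the assessments just described, which may mean only the coagulation reactions. Nothing links the forwarded reports to the analysed data.

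**Conclusion.** The point holds in a limited form. Section 11 promises more than Section 10 collects, and Sections 8.2, 8.3 and 10 do not agree on what is recorded. Non-coagulation reactions can become known individually, but as planned they cannot be quantified against exposure or compared by Protein C use, and a zero in an ADR table could not be read as evidence of safety.

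This rests on taking the confining sentence in Section 10 as the operative rule, and on the plan's silence about where forwarded reports are stored. If the eCRF already takes other reactions and they are tabulated, what remains is a conflict of wording. No numerical size can be derived from the documents; the 53% to 95% range depends wholly on the assumed risk. The point bears on the safety outputs and leaves the mortality analysis untouched.

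**What to change.** Reconcile Sections 8.2 (flowchart), 8.3, 10 and 11 in one of two ways.

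**Preferred.** State in Section 10 that bleeding and thrombotic reactions are the events of specific interest, and that any other suspected reaction or safety concern already forwarded under that section is also entered on the eCRF ADR page with event, suspected product, onset and outcome. Tabulate these entries by product in the biannual reports, beside the number exposed, and label them as spontaneously reported. Align Section 8.3 and the flowchart row with this wording. This does not require collection of all adverse events.

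**Alternative.** Keep the restriction, limit the Section 11 aim to coagulation-related reactions plus spontaneous reports, and state in every safety output that non-coagulation reactions were not systematically registered.

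**Cost.** The first option needs a protocol amendment and a short extra eCRF entry. The added site work should be small because the report must already be forwarded, though this cannot be confirmed without the eCRF. Data would be incomplete for patients enrolled before the amendment. Back-entry from earlier reports may fail where the anonymisation in Section 9 has already replaced patient numbers. Spontaneous reports will under-count, so any rate should be presented as a lower bound. The second option costs only text, but gives up any rate for non-coagulation reactions.

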Endpoints	
 
• All-cause in-hospital mortality
 
• Morbidity at defined post-diagnosis intervals and over 7 consecutive days 
 
- Mean total SOFA score (age <math>\geq 16</math>)
 
- PELOD score (age <math>< 16</math>)
 
- <math>\Delta</math>SOFA or dPELOD score for day-to-day comparisons
 
 
 
• Extent and severity of Purpura lesions
 
• Need for reconstructive surgery (amputations, skin grafts)
 
• Length of ICU stay (days)
 
• Length of hospital stay (days)
 
• Changes in hematological parameters 
 
- WBC count
 
- Thrombocyte count
 
- Hemoglobin
 
 
 
• Changes in coagulation parameters 
 
- Prothrombin time (PT)
 
- Activated partial thromboplastin time (aPTT)
 
- Fibrinogen
 
- D-dimers
 
- Thrombin-antithrombin complex (TATc)
 
- Protein C activity
 
- Antithrombin III activity
 
 
 
• Changes in inflammatory parameters 
 
- C-reactive protein (CRP)
 
- Procalcitonin (PCT)
 
- Interleukin 6 (IL-6)
 
 
 
• Changes in organ dysfunction parameters 
 
- Glucose
 
- Lactate
 
- Creatine kinase (CK)
 
 
 
• Duration of mechanical ventilation (days)
 
• Duration of renal replacement therapy (days)
 
• Vasopressor use (days/doses)
 
• Sepsis-inducing pathogen
 
• Adverse event related to PF treatment (reporting as per decision of the investigator) 
 
- Bleeding
 
- Thrombotic events
 
 
 

Inclusion criteria	
 
- Diagnosis of severe sepsis and Purpura fulminans
 
- Signed informed consent (according to local legal regulations)
 

Exclusion criteria	
 
- premature neonates (<math>< 36</math> gestational week)
 

Centers	Approx. 30 participating centers in Germany, Austria, Ireland, UK, Italy, Spain, Netherlands (selected centers)

Timetable	First patient in	Q3 2015
	Registry duration	3 years, with an option of prolongation
	Estimated enrolment	Approx. 50 patients/year
	Interim Analysis	Biannually

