## 6. Rationale and background

*Purpura fulminans* is a life-threatening and highly disabling condition characterized by rapidly evolving thrombosis in the dermal and systemic microcirculation. The estimated incidence of the disease is 0.1 per 100,000 inhabitants [Nicolas and Debonne, 2002]. It is associated with high mortality (above 50 %), owing to progressive cutaneous hemorrhage and multiple organ dysfunction. Profound tissue lesions and grave disturbance in numerous vital functions also determine a considerable long-term morbidity and disability.

Apart from a few cases of idiopathic origin, the etiology of *Purpura fulminans* is ascribed to either congenital abnormality or acquired deficiency of Protein C-operating anticoagulant pathways. The latter condition is in the vast majority secondary to an acute severe infection, thus coining the term sepsis-induced or sepsis-associated *Purpura fulminans* (SAPF) [Betrosian et al., 2006]. Several bacterial pathogens can induce SAPF, with meningococcal and pneumococcal infections accounting for the majority of cases. Causal involvement of viral and protozoan pathogens also has been described [Betrosian et al., 2006].

The pathogenesis of SAPF exemplifies the induction of a coagulopathy by the intertwined action of extrinsic bacterial (e.g. endotoxins) and intrinsic (e.g. vascular, inflammatory and hematologic) factors. The decay of endogenous anti-coagulant systems has a decisive contribution to the imbalance of clotting in sepsis and the presence of a consumptive coagulopathy is a distinct feature of infection-associated *Purpura fulminans* [Darmstadt, 1998]. Extensive similarities with clinical and pathological characteristics of *Purpura fulminans* in congenital Protein C deficiency have brought this endogenous anti-coagulant into focus with regard to the pathogenesis of SAPF [Francis, 1990]. Indeed, SAPF reflects an exaggerated pro-coagulant response resulting from decreased abundance/activity of endogenous anticoagulants, such as antithrombin and Protein C [Dempfle,

2004]. Meanwhile, ample evidence has accumulated in support of the view that circulating Protein C concentrations markedly decline in severe sepsis, due to both, suppressed biosynthesis and increased consumption/degradation [Fourrier et al., 1992; Leclerc et al., 1992; Borgel et al., 2006; Shorr et al., 2006].

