## **8. Research methods**

### **8.1. Study design**

The registry comprises prospective, open-label data collection on the current state of incidence and management of SAPF, regardless of the etiopathogenic background. Using appropriate statistical techniques, specific emphasis will be laid on the comparison of outcomes in therapeutic approaches including or avoiding supplementation with Protein C formulations.

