### 8.3. Variables

The selection of the endpoint all-cause in-hospital mortality is justified, in view of the exceptional severity of the disease *per se* and considerable risk associated with the subsequent management of its late sequelae (e.g. reconstructive surgery). On a case-by-case basis, a comparison with the probability of a lethal outcome, as defined by the APACHE II/ SAPS II or PRISM III score, will be made.

Changes in morbidity (as assessed by the SOFA or PELOD indices) will be presented by the difference between scores measured at admission and after 1, 3, 5 and 7 days upon being diagnosed with SAPF ( $\Delta$ SOFA, dPELOD), as well as by the mean total score (SOFA, PELOD) recorded over the observation period of 7 days.

Records will also include description of imminent surgical interventions (during the SAPF treatment), as well as reconstructive measures (skin grafting, amputation).

The sepsis-inducing pathogen and the primarily affected organ will be identified by the results of microbiological examinations and in accordance with clinical manifestations.

Further endpoints comprise the length of stay in the ICU and the total duration of hospitalization (including time of post-SAPF therapy).

Changes in hematological, coagulation and inflammatory parameters will be monitored at selected intervals across the treatment and serve as biomarkers of treatment efficacy or surrogate endpoints, as follows:

- Thrombocyte counts
- Leukocyte counts
- Hemoglobin
- Prothrombin time (PT)
- Activated partial thromboplastin time (aPTT)
- Fibrinogen
- D dimers
- Thrombin-Antithrombin complex (TATc)
- Protein C activity
- Antithrombin III activity
- C-reactive protein (CRP)
- Procalcitonin (PCT)
- Interleukin 6 (IL-6)

Several of these parameters have been used in clinical studies and shown significant changes in the course of therapeutic interventions in sepsis and Purpura fulminans [Bernard et al., 2001; de Kleijn et al., 2003; Schellongowski et al., 2006; Shorr et al., 2008].

Laboratory indices of organ dysfunction are confined to measurements of

- Glucose
- Lactate
- Creatine kinase

Recording of adverse events related to the treatment of SAPF is left at the discretion of the local site investigator (c.f. comment in 9.9. *Limitations of research methods*); the emphasis is laid on

- bleeding incidents
- thrombotic events

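### Bleeding and thrombosis are registered only when an unblinded investigator attributes them to treatment, so registered reaction rates cannot support an unbiased harm comparison by Protein C use; the direction of the bias is unknown

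*Combined protocol and SAP*

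**What the plan says.** Section 10 sets the scope of safety data in two steps. First, "the documentation and reporting of all adverse events (AE) and serious adverse events (SAE) occurring in these patients is beyond the scope of this registry". Second, "registration of treatment-emergent adverse drug reactions (ADR) will be confined to those, which denote pathological alteration of the coagulation status", with bleeding and thrombotic events named as the reactions of specific interest. Sites enter them in the eCRF, "with the local investigator being responsible for the assessment of the ADR". No independent or blinded adjudication is described.

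The endpoint list in the Abstract has the same filter: "Adverse event related to PF treatment (reporting as per decision of the investigator". Section 8.3 repeats it: "Recording of adverse events related to the treatment of SAPF is left at the discretion of the local site investigator". The flowchart in 8.2 has one row for adverse drug reactions, completed once, at end of study.

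Section 8.1 says "The registry comprises prospective, open-label data collection on the current state of incidence and management of SAPF" and that "specific emphasis will be laid on the comparison of outcomes in therapeutic approaches including or avoiding supplementation with Protein C formulations". Section 8.7 applies descriptive analysis with 95% confidence intervals to all endpoints and describes between-group comparisons. Section 11 bases therapy recommendations on the biannual evaluations together with safety records.

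**The concern.** The attribution is part of the event definition. A bleed or thrombosis that the investigator ascribes to the disease is not a drug reaction and does not enter the registry as an outcome. In this disease the distinction is hard to draw. Section 6 describes a condition "characterized by rapidly evolving thrombosis in the dermal and systemic microcirculation", with consumptive coagulopathy and progressive hemorrhage, and 8.9 concedes that combined therapy may obscure the effect of any single agent.

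If the chance of attribution differs between patients who did and did not receive Protein C, the registered rates differ even when the true risks are equal, or agree when the true risks differ. This is separate from whether recording is mandatory or discretionary: a site that faithfully entered every attributed event would still pass it through the same filter. At stake are any harm contrast by Protein C use and the recommendations in section 11 that would draw on it. Section 8.9 does not list this limitation.

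**Working it through.** **Is there another route by which the events are counted?**

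- Cutaneous manifestations: yes. The flowchart has a purpura lesion assessment at baseline and days 1, 3, 5 and 7, the Annex maps petechiae, ecchymosis, bullae and necrosis or gangrene, and purpura-related surgery is recorded. None of these needs attribution to a drug.
- Intracranial or visceral bleeding and thrombotic events other than the purpura: no flowchart row records them irrespective of cause.
- Section 10 also has sites forward other safety concerns whatever their causality. This report goes to the Marketing Authorization Holder and the Advisory Committee and is not described as an outcome variable or a systematic count.

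The gap therefore concerns non-cutaneous events in the eCRF data.

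**Size of the distortion**

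The plan states no event rate, attribution rate or harm effect, so there is no figure of its own to reproduce. Let p1 and p0 be the true risks in users and non-users, and a1 and a0 the probabilities that an event is attributed and so registered.

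- Registered risk = p × a.
- Observed RR = (p1 × a1) / (p0 × a0) = true RR × (a1 / a0).

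With equal true risk (true RR 1), for assumed attribution in users versus non-users:

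- 50% vs 50%: RR 1.0
- 50% vs 40%: 0.50/0.40 = 1.25
- 50% vs 25%: 0.50/0.25 = 2.0
- 25% vs 50%: 0.25/0.50 = 0.5

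A true difference can also be hidden. A true RR of 0.5 with attribution 50% vs 25% gives 0.5 × 2.0 = 1.0. A true RR of 2.0 with attribution 25% vs 50% gives 2.0 × 0.5 = 1.0.

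**How often would this look like a finding?**

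Inputs: about 50 patients a year for 3 years (Abstract, timetable) gives 50 × 3 = 150. Assumed: a 75/75 split, the same true risk in both groups, and a two-sided Fisher test at 0.05. The plan names no test for this endpoint, so Fisher's test is only a yardstick. At a true risk of 20%, 75 × 0.20 = 15 events are expected per group. Attribution of 50% vs 25% registers 7.5 and 3.75 of them, that is 10% vs 5%. Exact probabilities of a significant difference in the false direction:

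| Attribution, users vs non-users | True risk 20% | True risk 30% |
|---|---|---|
| 50% vs 50% (per direction) | 1.3% | 1.5% |
| 50% vs 40% (false harm) | 3.5% | 4.9% |
| 50% vs 25% (false harm) | 12.8% | 22.9% |
| 25% vs 50% (false protection) | 12.8% | 22.9% |

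The last two rows mirror each other: the size depends on the attribution ratio, and the sign on which group has the higher attribution.

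**After the change**

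If all events are recorded with equal completeness in both groups, a1 = a0, so observed RR = true RR and the attribution component of the bias is zero.

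**The case against.** A reader might infer that the contrast is biased against Protein C, because a recipient always has that product as a suspect and a non-recipient may have none. The documents do not support that as a statement of fact. The filter is relatedness to any treatment of the condition, not to Protein C. Sections 6 and 8.2 list heparin, antithrombin and plasma products among the agents in use, so non-users may well have a suspect product. An investigator who chose Protein C may ascribe a bleed to the disease. For thrombosis the asymmetry is weaker still: the protocol treats Protein C as an anticoagulant, and a thrombosis under an anticoagulant is easily read as disease. This objection stands, and the direction must be left open.

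A reader might also infer that a formal harm test by Protein C use is planned. It is not. The all-endpoints rule in 8.7 is descriptive, the research objectives stratify morbidity and mortality by Protein C use without naming adverse events, and 8.5 warns that treatment comparisons may be feasible only for selected endpoints. The harm contrast is an inference from 8.1, 8.7 and section 11. It is a reasonable one, since even descriptive rates by use and non-use would carry the distortion into the recommendations.

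Finally, limiting adverse event collection in critically ill patients is a reasoned choice. That stands too, and it constrains the remedy: only the two event types already named should be added. Because the disease is itself disseminated thrombosis, a thrombotic event must be defined apart from the purpura. Counting all events without regard to timing would charge events before the first Protein C dose to the treated group.

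**Conclusion.** The concern holds in limited form. In the eCRF data, non-cutaneous bleeding and thrombosis are registered only after attribution by an unblinded local investigator. That attribution may differ by Protein C use, so registered reaction rates cannot support an unbiased harm comparison between use and non-use.

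The direction is unknown: bias against Protein C is plausible for bleeding, less certain for thrombosis, and could reverse. The size is also unknown. A twofold difference in attribution doubles or halves the risk ratio, and equal attribution leaves it unbiased. These figures rest wholly on assumed attribution rates, and the false-finding probabilities also on an assumed event risk, group split and test. The need for the change does not depend on the sign. The sponsor should make it; confidence that the problem is material is medium.

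**What to change.** **Section 10, 8.3 and the flowchart.** For every patient, record whether bleeding (especially intracranial or visceral) occurred, and whether a thrombotic event distinct from the mapped purpura lesions occurred, with onset date and severity, irrespective of presumed cause. Give a short case definition for the thrombotic event. Enter the investigator's causality judgement and the suspect product as separate fields.

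**Section 8.7.** Base any comparison by Protein C use on these all-cause events. Use onset date relative to first Protein C administration, so that earlier events are not counted as exposed; if the eCRF does not already hold that start date, add it. Report attributed reactions per product only, not as a use versus non-use contrast.

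**Section 8.9.** State that confounding by indication and differences in detection or survival remain.

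All other adverse events and serious adverse events stay out of scope, and forwarding of suspected reactions is unchanged.

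**Cost.** Two event items with date and severity on the existing eCRF, and a few sentences in the protocol. The downside is slightly more site documentation, and counts that include disease-related events.
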